13.3. Subgroup Analysis

No subgroup analysis is planned for this study.

13.4. Interim Analysis

An unblinded interim analysis will be conducted after the 6th subject in each study arm has completed period 2. The objectives of this interim analysis are to:

1. Stop the study early for overwhelming evidence of early efficacy, as defined above in Section [13.2.1](#).

2. Continue the study enrolling either 3 or 6 additional subjects per study arm depending on the outcome of the interim analysis (see Section [13.2.1](#))

The unblinded statistician not related to the conduct of the study will perform this interim analysis according to a DSMB charter that will define the analysis details and the communications between the unblinded statistician, the DSMB, and the sponsor.

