13. DATA ANALYSIS AND STATISTICAL METHODS

13.1. Sample Size Determination

This is a parallel group adaptive design with one interim analysis after 6 subjects in each study arm have completed their post-treatment success-failure determination. Depending on the comparison of the treatment and placebo failure rates, the study will either be stopped with an early claim for treatment efficacy, or continued with either 3 or 6 additional subjects per study arm so that the final comparison of failure rates will be based on 9 or 12 subjects per study arm. The final sample size will be based on the outcome of the interim analysis.

The criteria for stopping early at 6 subjects per group or continuing to a final sample size of 9 or 12 subjects per group was designed so that the type 1 error is no larger than 0.025 for treatment = control failure rates at any failure rate. The overall power for concluding that the treatment failure rate is less than control is over 98% if the placebo failure rate is at least 0.9 and the treatment rate is no more than 0.1, with early efficacy having a power of 66%. If the placebo failure rate is at least 0.95 and the treatment failure rate is no more than 0.05 then the chance for an early efficacy determination is 88%.

Power and type 1 error levels were computed using Monte Carlo simulations of the study, 10,000 replications for each determination (R, version 3.1.2).

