13.2.1. Primary Endpoint (Pharmacodynamic)

For each subject, the average GIR will be computed for periods 1 (baseline), 2 (treatment) by determining the area under the curve of GIR excluding the first 2 hours versus time and then dividing by the time duration for each of the periods excluding the first 2 hours using the last 24 hours for each period, or if less than 24 hours is available, the available data excluding the first 2 hours.

The primary comparison of treatment and placebo will be based on a success-failure determination (see Section 5.1).

This is a parallel group, adaptive design with one interim analysis after 6 subjects in each study arm have completed their success-failure determination. If, at the interim analysis, the observed

treatment failure rate is lower than placebo so that the one-tailed p value is less than or equal to 0.0124 (Fisher's exact test, hypergeometric distribution based on the total number of failures) then the study will be stopped due to early treatment efficacy.

If this interim one-tailed p value is greater than 0.0124 but less than or equal to 0.05, then the study will continue and an additional 3 more subjects per study arm will be randomized. If this interim one-tailed p value exceeds 0.05 then the study will continue, and an additional 6 more subjects will be randomized. The final analysis will be based on the observed treatment and placebo failure rates using all subjects with a success-failure determination. If, at the final analysis, the observed treatment failure rate is lower than placebo so that the one-tailed p value is less than or equal to 0.04 (hypergeometric distribution) then treatment efficacy will be established.

The actual type 1 errors are smaller than the efficacy criteria would suggest because of the small sample sizes and the use of Fisher's exact test. From Monte-Carlo simulations the overall type 1 error for this design is bounded above by 0.016 for null hypothesis treatment = placebo failure rates at any failure rate using the above criteria. The type 1 error achieves its maximum at treatment = placebo = 0.5, and for this design the maximum is 0.016 as estimated by 10,000 Monte Carlo replications of the design.

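### The interim has no pre-specified futility outcome: every p above 0.05 adds 6 infants per arm, even when the final p≤0.04 can no longer be reached

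*Combined protocol and SAP*

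**What the plan says.** Section 13.1 sets "one interim analysis after 6 subjects in each study arm have completed their post-treatment success-failure determination". Section 13.2.1 then gives three branches, based on a one-tailed Fisher test of failure counts:

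- Stop for efficacy if the "treatment failure rate is lower than placebo so that the one-tailed p value is less than or equal to 0.0124".
- Add 3 per arm: "If this interim one-tailed p value is greater than 0.0124 but less than or equal to 0.05, then the study will continue".
- Add 6: "If this interim one-tailed p value exceeds 0.05 then the study will continue, and an additional 6 more subjects will be randomized". This sentence does not say per arm, but 13.1 and 13.4 do.

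The "final comparison of failure rates will be based on 9 or 12 subjects per study arm" (13.1), and efficacy is claimed if failures over both stages are rarer on glucagon, "so that the one-tailed p value is less than or equal to 0.04 (hypergeometric distribution) then treatment efficacy will be established" (13.2.1). Section 13.4 lists two objectives for the interim: "Stop the study early for overwhelming evidence of early efficacy", and "Continue the study enrolling either 3 or 6 additional subjects per study arm depending on the outcome of the interim analysis". Neither section, nor any other part of the document, states a futility or conditional-power rule.

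There are non-numerical routes to stopping. Section 15.4 has the DSMB review cumulative safety and efficacy data. It may advise on continuing from a safety standpoint and make other recommendations on study conduct. Section 18.2 lets the sponsor terminate at its discretion. Section 13.4 leaves the details of the interim analysis to a DSMB charter that is not part of this document.

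**The concern.** The branch for p above 0.05 has no lower limit. It treats a promising but inconclusive interim and one in which glucagon failed more often than placebo in the same way: both add 12 infants. Some of the unfavourable tables leave the final test with no route to p≤0.04, whatever the second stage shows.

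The infants concerned are under 1 year old. Under Section 10.2.1 they have octreotide and diazoxide withdrawn and are weaned until glucose has dropped below 70 mg/dL at least twice. They then enter a placebo-controlled period of 24 or 48 hours. If the primary comparison is already lost, those infants can contribute to safety, device and secondary estimates but not to the question the trial was sized for. The protocol should at least ensure that the DSMB is told when this has happened.

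**Working it through.** **Inputs.** 6 evaluable infants per arm at the interim (13.1); cut-offs 0.0124 and 0.05 at the interim and 0.04 at the end (13.2.1); 9 or 12 per arm at the end (13.1). Write t for glucagon failures and c for placebo failures. For arms of size n and F failures in total, the one-tailed p is the sum over k = 0 to t of C(n,k)·C(n,F−k)/C(2n,F).

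**Step 1: reproduce the plan's figures.** The early-stop tables (t vs c) are 0 vs 5 (p=0.0076), 0 vs 6 (p=0.0011) and 1 vs 6 (p=0.0076).

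- At failure rates 0.1 and 0.9, 0.9⁶ = 0.5314 and 6×0.1×0.9⁵ = 0.3543. The chance of stopping early is 0.5314² + 2×0.5314×0.3543 = 0.659 (stated 66%).
- At 0.05 and 0.95 the same sum is 0.7351² + 2×0.7351×0.2321 = 0.882 (stated 88%).
- Exact overall power at 0.1 against 0.9 is 99.0% (stated over 98%).
- Exact type 1 error is 0.0168 at 0.5, with a maximum of 0.0169 near 0.585. The stated 0.016 is within simulation error for 10,000 replications (standard error about 0.0013), and all are below 0.025.

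The design has therefore been read as intended.

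**Step 2: classify the interim tables.** There are 7×7 = 49. Three stop, three add 3 per arm (0 vs 4, 1 vs 5, 2 vs 6), and 43 add 6 per arm.

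**Step 3: find the best final p for each continuing table.** All second-stage results were enumerated. The smallest p arises when every new glucagon infant succeeds and every new placebo infant fails, giving t/12 against (c+6)/12.

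- 3 vs 2 becomes 3/12 vs 8/12: (12 + 792 + 14,520 + 108,900)/2,496,144 = 0.0498. Out of reach.
- 1 vs 0 becomes 1/12 vs 6/12: (792 + 11,088)/346,104 = 0.0343. Still reachable.

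| Interim (glucagon vs placebo failures) | Best final p |
|---|---|
| 1 vs 0; 6 vs 5 | 0.0343 |
| 2 vs 1; 5 vs 4 | 0.0447 |
| 3 vs 2; 4 vs 3 | 0.0498 |
| 2 vs 0; 6 vs 4 | 0.0965 |
| all other tables with t > c | 0.107 or more |

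There are 21 tables with t > c. Removing 1 vs 0 and 6 vs 5 leaves 19 that cannot reach 0.04. All 19 lie in the branch that adds 6 per arm, so each leads to 12 more infants.

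**Step 4: how likely they are.** With equal failure rates, the chance is [1 − P(tie)]/2 − P(1 vs 0) − P(6 vs 5). At 0.9 this is (1 − 0.4179)/2 − 0.0000 − 0.5314×0.3543 = 0.2911 − 0.1883 = 0.103.

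| Failure rates (glucagon, placebo) | Chance of an unreachable table |
|---|---|
| 0.95, 0.95 | 3.2% |
| 0.9, 0.9 | 10.3% |
| 0.8, 0.8 (assumed) | 25.2% |
| 0.7, 0.7 (assumed) | 34.0% |
| 0.5, 0.5 (assumed) | 38.4% |
| 0.1, 0.9 (design alternative) | 0.005% |

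**Step 5: effect of stopping there.** These tables never lead to rejection, so power (99.0%) and type 1 error are unchanged. Expected total size falls by 12 times the chance above: from 24.0 to 22.8 at 0.9 (12×0.103 = 1.2), from 23.9 to 19.8 at 0.7, and from 23.9 to 19.3 at 0.5.

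**Step 6: sensitivity to the counts.** With one extra evaluable infant in either arm (13 vs 12 or 12 vs 13), the best p for 2 vs 1, 3 vs 2, 4 vs 3 and 5 vs 4 falls to 0.029–0.036, so these four tables become winnable. They carry 3.6 of the 10.3 percentage points at 0.9, and 19 of the 38 at 0.5.

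**The case against.** Omitting a futility rule is a legitimate choice in a small proof-of-concept trial. It contradicts nothing in the plan and harms neither power nor type 1 error. Later infants still inform safety, device performance and the other secondary objectives in Section 5.2. Blinded treatment lasts at most 48 hours, infants without a 20% reduction at 24 hours move early to open-label glucagon, and all are eligible for that phase (7.1). All of this stands, and it makes the point an improvement to the plan rather than an error in it.

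Three stronger readings are tempting, and the documents do not support them.

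- *The plan unavoidably enrols 12 more infants.* Section 8.3 halts randomisation pending the interim result, 18.2 allows the sponsor to terminate, and the charter may contain more. What is missing is a pre-specified prompt, not the power to stop.
- *The DSMB may act on safety alone.* Section 15.4 also gives it efficacy data and a remit for other recommendations on study conduct.
- *19 of 49 means a 39% chance.* The tables are not equally likely. At the placebo failure rate the plan assumes (0.9 or more), an ineffective drug gives about 10% or less.

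A table such as 3 vs 2 is also not evidence that glucagon is harmful. It is within chance variation, and only the arithmetic of the final test is settled.

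Finally, unreachable holds strictly only for 6 then 12 evaluable infants per arm. Section 9.1 replaces non-evaluable infants under minimisation, 13.4 waits for the sixth completer in each arm, and 13.2.1 analyses everyone with a determination. Counts may therefore overrun, and a fixed list of tables would be fragile.

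**Conclusion.** The point holds in this form: Sections 13.2.1 and 13.4 pre-specify no outcome for an interim from which the final criterion cannot be met. With exactly 6 then 12 evaluable infants per arm, and 6 added per arm when p exceeds 0.05, that covers 19 of the 49 tables: glucagon failures exceed placebo failures, except 1 vs 0 and 6 vs 5.

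The practical size is modest under the plan's own assumptions. It is about 10% if glucagon has no effect and both failure rates are 0.9, 3% at 0.95, and negligible if the drug works as planned. It is substantial (25–38%) only if failure rates under no effect lie between 0.8 and 0.5, values the plan does not assume. The primary inference is valid as it stands. A stop costs it nothing, so this is a cheap change worth making.

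**What to change.** Add a third, non-binding outcome to 13.2.1, 13.4 and the DSMB charter. At the interim, the unblinded statistician takes the actual evaluable counts in each arm, the infants already randomised but not yet determined, and the planned additions. If no possible second-stage result gives a final one-tailed p≤0.04, the statistician tells the DSMB, which may then recommend stopping randomisation.

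Define the rule by that calculation. Give the 19 tables only as an illustration for exactly 6 then 12 per arm, and recompute if the counts or the final cut-off change. State in 13.2.1, as 13.1 and 13.4 already do, that the additional 6 are per arm.

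The cost is a sentence or two in the protocol and charter. The enrolment pause, the unblinded statistician and the DSMB already exist. Power and type 1 error do not change. The downside is fewer infants for safety, device and secondary estimates when the rule is used. Because it is non-binding, the DSMB may still recommend continuing for those reasons.

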14. QUALITY CONTROL AND QUALITY ASSURANCE

During study conduct, Xeris Pharmaceuticals or its agent will conduct periodic visits to ensure that the protocol and Good Clinical Practices are being followed. The monitor may review source documents to confirm that the data recorded on CRFs is accurate. The investigator and institution will allow Xeris Pharmaceuticals' monitor, and appropriate regulatory authorities, direct access to source documents to perform this verification.

The study site may be subjected to review by the institutional Review Board and/or to quality assurance audits performed by Xeris Pharmaceuticals, and/or to inspection by appropriate regulatory authorities. It is important that the investigator and study staff are available during the monitoring visits and possible audits or inspections and that sufficient time is devoted to the process.

15. DATA HANDLING, RECORD KEEPING, MONITORING AND AUDITS

15.1. Case Report Forms/Electronic Data Record

As used in this protocol, the term “case report form” (CRF) should be understood to refer to either a paper form or an electronic data record, or both. A complete set of CRFs is required and should be completed for each individual subject. The completed original CRFs are the property of Xeris Pharmaceuticals and should not be made available in any form to third parties, except for authorized representatives of Xeris Pharmaceuticals or appropriate regulatory authorities, without written permission from Xeris Pharmaceuticals.

The investigator has the responsibility for the collection and reporting of all clinical, safety and laboratory data entered on the CRFs and any other data collection forms (source documents) and ensuring that these are accurate, authentic, attributable, complete, consistent, legible, contemporaneous, enduring and available when required. The CRFs must be signed by the investigator or by an authorized staff member to attest that the data contained in the CRFs is true.

In many cases, data will be entered directly into electronic CRFs (eCRFs) as part of a web-based electronic data collection (EDC) system. When data are entered directly, eCRFs will be considered as source documents. Other electronic data will be uploaded into the EDC system directly from downloads of devices or from datasets provided by laboratories that are processing blood samples. These electronic data will be considered as source documents.

Other data will be collected first on paper worksheets or CRFs and then transcribed into the EDC system. In such cases, the paper forms will be considered source documents for the electronic entries. In some cases, source documents are hospital records or the subject’s chart. In these cases, data collected in the CRFs must match the data in those charts. A document should be available that clearly identifies which data are being entered directly into the electronic CRF, and which data have a paper source.

Any corrections to entries made in the CRFs must be dated, initialed and explained (if necessary) and should not obscure the original entry. An equivalent electronic process will be utilized for changes to eCRFs or other changes to data entered into the EDC system.

15.2. Records Retention

To enable evaluations and/or audits from regulatory authorities or Xeris Pharmaceuticals, the investigator agrees to keep records, including the identity of all participating subjects (sufficient information to link records, e.g., CRFs and hospital records), all original signed informed consent documents, copies of all CRFs, safety reporting forms, source documents, and detailed records of treatment disposition, and adequate documentation of relevant correspondence (e.g., letters, meeting minutes, telephone calls reports). The records should be retained by the investigator according to the International Conference on Harmonisation (ICH), regulations, or as specified in the Clinical Study Agreement, whichever is longer. The investigator must obtain Xeris Pharmaceuticals’ written permission before disposing of any records, even if retention requirements have been met.

15.3. Monitoring

Monitoring and auditing procedures developed by Xeris Pharmaceuticals and/or its designee will be implemented to ensure compliance with FDA and ICH GCP and GLP guidelines.

The Xeris Pharmaceuticals' designated representative (the monitor or auditor) will contact the investigator and conduct regular visits to the clinical site. The monitor will be expected and allowed to verify the investigator's qualifications, to inspect clinical site facilities, and to inspect study records, including proof of IRB review, with the stipulation that subject confidentiality will be maintained in accordance with local and federal regulations, including HIPAA requirements. The monitor will also be responsible for confirming adherence to the study protocol, inspecting CRFs and source documents, and ensuring the integrity of the data. CRFs will be checked for accuracy, completeness, and clarity and will be cross-checked for consistency with source documents, including laboratory test reports and other subject records. Instances of missing or uninterpretable data will be resolved in coordination with the investigator.

The monitor/auditor will also investigate any questions concerning adherence to regulatory requirements. Any administrative concerns will be clarified and followed. The monitor will maintain contact with the site through frequent direct communications with the study site by e-mail, telephone, facsimile, and mail. The investigator and all other site personnel agree to cooperate fully with the monitor and will work in good faith with the monitor to resolve any and all questions raised, and difficulties detected by the monitor.

15.4. Data Safety Monitoring Board

An independent Data Safety Monitoring Board (DSMB) will have oversight of this study. The DSMB is an expert advisory group of physicians who function as a review committee independent from the Sponsor, and who function to ensure the safety of subjects enrolled in the study. DSMB members will meet periodically, without the Sponsor or study team members present, to review and discuss cumulative safety and efficacy data.

After the review of each Data Report has been completed, the DSMB Chairperson will provide the official DSMB recommendation to Sponsor regarding the appropriateness of continuing the study, from a safety perspective, as well as any other recommendations relevant to study conduct and/or patient safety.

The operating procedures of the DSMB are based on and are in compliance with the Food and Drug Administration's "Guidance for Clinical Trial Sponsors [on the] Establishment and Operation of Clinical Trial Data Monitoring Committees" (March 2006, OMB Control Number: 0910-0581) and with the European Medicines Agency's "Guideline on Data Monitoring Committees" (January 2006, EMEA/CHMP/EWP/5872/03 Corr).

15.5. Audits and Inspections

The investigator understands that regulatory authorities, the IRB, and/or Xeris Pharmaceuticals or their designees have the right to access all CRFs, source documents, and other study documentation for on-site audit or inspection and will retain this right from the start of the study to at least 2 years after the last approval of a marketing application or for at least 2 years after clinical development of the study drug for the indication being studied has been discontinued.

The investigator is required to guarantee access to these documents and to cooperate with and support such audits and inspections.

16. ETHICAL CONSIDERATIONS

16.1. Conduct

This protocol is written in accordance with the principles established by the 18th World Medical Assembly General Assembly (Helsinki, 1964) and amendments and clarifications adopted by the 29th (Tokyo, 1975), 35th (Venice, 1983), 41st (Hong Kong, 1989), 48th (Somerset West, South Africa, 1996), 52nd (Edinburgh, 2000), 53rd (Washington, 2002), 55th (Tokyo, 2004), and 59th (Seoul, 2008) General Assemblies. The investigator will ensure that the study described in this protocol is conducted in full conformance with those principles, the protocol, current FDA regulations, ICH Good Clinical Practices (GCP) guidelines, Good Laboratory Practices (GLP) guidelines, local ethical and regulatory requirements, including the Federal Food, Drug and Cosmetic Act, U.S. applicable Code of Federal Regulations (title 21), and IRB/IEC requirements relative to clinical studies.

Should a conflict arise, the investigator will follow whichever law or guideline affords the greater protection to the individual subject. The investigator will also ensure thorough familiarity with the appropriate administration and potential risks of administration of the study drug, as described in this protocol and the Investigator's Brochure, prior to the initiation of the study.

16.2. Institutional Review Board (IRB)

The Ethics Committee/IRB must be a properly constituted board or committee operating in accordance with 21 CFR Part 56, "Institutional Review Boards." This protocol, any protocol amendments, the associated informed consent forms, and the informed consent procedures must be submitted to the IRB for review and approved before the enrollment of any subject into the trial. Clinical supplies may not be shipped to the investigator until Xeris Pharmaceuticals has received a copy of the letter or certificate of approval from the IRB for the protocol and any protocol amendments.

All types of subject recruitment or advertising information must be submitted to Xeris Pharmaceuticals or its designee and to the IRB for review and approval prior to implementation. IRB approval of any protocol amendments must be received before any of the changes outlined in the amendments are put into effect, except when the amendment has been enacted to eliminate a potential hazard to study subjects. In such cases, the chair of the IRB should be notified immediately, and the amendment forwarded to the IRB for review and approval.

It is the responsibility of the investigator to have prospective approval of the study protocol, protocol amendments, informed consent documents, and other relevant documents, e.g., recruitment advertisements from the IRB. All correspondence with the IRB should be retained in the Investigator File. Copies of IRB approvals should be forwarded to Xeris Pharmaceuticals.

